1.1.2 Secondary Objectives

- 1.1.2.1 To study the safety and tolerability of everolimus in patients with BHD-associated localized renal tumors.
- 1.1.2.2 To assess changes in tumor growth rates and ability to delay surgical management in BHD patients.
- 1.1.2.3 To assess progression-free survival (PFS) and overall survival (OS).
- 1.1.2.4 To evaluate the effect of everolimus on mTOR activity in renal tumors (using pre- and on-treatment biopsies when available).
- 1.1.2.5 To assess the effect of therapy on BHD associated lung cysts and cutaneous fibrofolliculomas.

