3 STUDY IMPLEMENTATION

3.1 STUDY DESIGN

This is an open label, phase II study to evaluate the efficacy and safety of everolimus therapy in patients with BHD. Up to 16 evaluable patients will be enrolled.

Patients with BHD typically have bilateral, multifocal tumors localized to the kidneys. In general, the growth rates of these tumors is relatively slow and they are not expected to pose a risk of metastatic spread when the size of the tumors is <3cm. Most of these patients have a surgical option (partial nephrectomy) and are less willing to accept side effects than are patients with metastatic disease. Therefore, everolimus will be administered at a starting dose of 5mg PO QD. If the following criteria are met at the time of the first restaging evaluation, the dose will be escalated to 10mg PO QD.

- A) The patient has not had a complete or partial response, and
- B) The patient has not experienced grade 2 or greater toxicity attributable to everolimus

Restaging will be performed approximately every 12 weeks. Treatment can continue for up to 52 weeks in the absence of unacceptable toxicity or disease progression, except in patients with metastatic RCC associated with BHD in whom everolimus will be continued until disease progression or unacceptable toxicity.

All dosages prescribed and dispensed to the patient and all dose changes during the study must be recorded.

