3.4 STUDY CALENDAR

1 cycle = 28 days

Evaluations below may be performed within \pm 3 days of indicated time in order to accommodate patient schedules, holidays and weather emergencies. Imaging studies and optional tumor biopsies may be performed within \pm 7 days of indicated time.

Baseline and Restaging evaluation will be performed at the NIH CC. However, mandated laboratory studies and other evaluations may be performed at local laboratory or by local health care providers.

Restaging will be performed approximately every 12 weeks. Treatment can continue for 52 weeks in the absence of unacceptable toxicity or disease progression.

Patients with BHD associated tumors localized to the kidneys will be treated for one year in the absence of unacceptable toxicity or disease progression. Patients with locally advanced or metastatic disease will be treated until disease progression in the absence of unacceptable toxicity.

Abbreviated Title: Phase II everolimus for BHD

Version Date: March 7, 2017

	Screening / Baseline	Day 1	Cycle 1 Day 14	Cycle 2 Day 1	Cycle 2 Day 14	Cycle 3 Day 1	Cycle 3 Day 14	Cycle 4 Day 1	Start of Every Cycle	EOT	Follow up ¹¹	Survival ¹²
Visit no.	1	2	3	4	5	6	7	8	9, 10 etc...		EOT + 28 days	
Treatment days	-14 to -1											
Demography/informed consent	X											
Relevant medical history/current medical conditions	X											
Diagnosis and extent of cancer	X											
Vital signs	X	X*		X		X		X	X	X		
Height	X											
Weight	X	X*		X		X		X	X	X	X	
Physical examination	X ⁸											
ECOG/Karnofsky performance status	X	X*										
EKG ¹	X											
Thyroid function tests	X		Every 12 weeks									
CBC with differential	X		X	X		X		X	X	X	X	
Serum Chemistries ²	X		X	X		X		X	X	X	X	
Fasting serum Lipid Profile ³	X			X		X		X	X	X		
Urinalysis ⁴	X			X		X		X	X			
Serum β hCG (in female patients of childbearing potential)	X			X		X		X	X			
HbA1c, pulse oximetry	X											
PT/PTT	X											

Abbreviated Title: Phase II everolimus for BHD

Version Date: March 7, 2017

	Screening / Baseline	Day 1	Cycle 1 Day 14	Cycle 2 Day 1	Cycle 2 Day 14	Cycle 3 Day 1	Cycle 3 Day 14	Cycle 4 Day 1	Start of Every Cycle	EOT	Follow up ¹¹	Survival ¹²
Visit no.	1	2	3	4	5	6	7	8	9, 10 etc...		EOT + 28 days	
Treatment days	-14 to -1											
Prior/concomitant medications	X											
Adverse events												
Tumor evaluation												
PFT	X											
CT chest/abdomen/pelvis and/or, CT chest plus MRI abdomen/pelvis ⁵	X									X		

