5. Chest, abdomen, pelvis scans need to be repeated at each tumor assessment visit (including if negative at baseline). Scans for complete and partial responses must be repeated at least at 4 weeks but no later than the next scheduled tumor assessment following the first documented response. Skin lesions should be photographed in addition to measuring.																								
6. CT Neck in patients with known or suspected metastatic disease in the neck will be repeated at restaging if positive for metastasis.																								
7. A bone scan or skeletal survey is to be performed at baseline and will be repeated at restaging if positive for metastasis.																								
8. Repeat at restaging only if indicated																								
9. All patients should be screened for hepatitis risk factors and any past illnesses of hepatitis B and hepatitis C as outlined in Sections 2.2. Patients with viral hepatitis B or C risk factors should be screened for Hep B and HCV RNA-PCR.																								
10. Patients on antiviral prophylaxis treatment or positive HBV antibodies should be tested for HBV-DNA every 3 – 4 weeks. Patients with positive HCV-RNA PCR or a history of past infection, even if treated and considered 'cured' – should be followed by HCV-RNA PCR every 4 – 8 weeks.																								
11. Follow up visits conducted at the EOT+28 days visit.																								
12. After progression, an attempt will be made to follow patients to obtain information about survival every three to six months.																								
Legend: wks stands for weeks, EOT for End of Treatment visit																								
13. Photographic evaluation of skin lesions - only in patients with BHD- associated cutaneous manifestations.																								

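### Survival contact is scheduled only after progression, so OS follow-up beyond about week 57 depends on the patient's outcome; extending it to every treated patient is a cheap improvement to a secondary objective

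*Combined protocol and SAP*

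**What the plan says.** Section 1.1.2 lists as a secondary objective "To assess progression-free survival (PFS) and overall survival (OS". Section 8 covers only the response rate and gives no OS or PFS analysis.

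Survival contact has one row in the Study Calendar (Section 3.4), governed by footnote 12: "After progression, an attempt will be made to follow patients to obtain information about survival every three to six months". No other section schedules it.

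How long a patient stays under scheduled observation otherwise depends on disease extent:

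- **Localized.** The calendar section says "Patients with BHD associated tumors localized to the kidneys will be treated for one year", absent progression or unacceptable toxicity.
- **More advanced.** The same section says "Patients with locally advanced or metastatic disease will be treated until disease progression in the absence of unacceptable toxicity". Section 3.1 lifts the 52-week limit for a narrower group: "except in patients with metastatic RCC associated with BHD in whom everolimus will be continued until disease progression or unacceptable toxicity".

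After treatment, footnote 11 says "Follow up visits conducted at the EOT+28 days visit". Section 3.5 describes a safety visit 4-5 weeks after the drug is stopped and lists no imaging for it. Other later contact is conditional:

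- Footnote 5 requires confirmation of responses: "Scans for complete and partial responses must be repeated at least at 4 weeks but no later than the next scheduled tumor assessment".
- Section 3.5 follows unresolved grade 3-4 adverse events and collects outside scans where possible.
- Section 6.2.4.3 asks for effort to document progression after symptomatic deterioration.

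Section 3.6.2 takes patients off study when follow-up is complete but does not say how long follow-up lasts.

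**The concern.** Followed to the letter, the plan makes scheduled OS follow-up after about week 57 conditional on an outcome. Progressors keep being contacted. Localized patients who finish without progressing do not, and Section 3.1 describes localized disease as typical. In a Kaplan-Meier estimate those patients are censored at about month 13, so the later part of the curve comes from progressors and from advanced-disease patients still on treatment.

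If death is more frequent after progression, the later curve is too low. If it is not, the curve is unbiased but rests on fewer patients than were treated. At stake is whether the trial can report OS beyond roughly one year.

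**Working it through.** **1. The plan's own figures.** The documents state no figure for OS or PFS. The response design reproduces: stopping at 0 of 12 when the rate is 5% has probability 0.95^12 = 54.0%, and expected size is 12 + 4 x (1 - 0.540) = 13.8. Success at 3 or more of 16 gives power 80.1% at a 25% rate. None of this uses survival follow-up.

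**2. Last scheduled contact, localized completer.** 52 + 4 = week 56 (footnote 11); 52 + 5 = week 57 (Section 3.5, upper end).

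**3. How many remain under scheduled contact.** Let f be the share with advanced disease and q the share of localized patients who progress on treatment. Neither is in the documents; both are assumed. Number remaining = 16 x [f + (1 - f) x q], before deaths.

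| f | q | Remaining of 16 |
|---|---|---|
| 0 | 10% | 1.6 |
| 0 | 20% | 3.2 |
| 0 | 30% | 4.8 |
| 25% | 10% | 5.2 |
| 25% | 30% | 7.6 |

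Simulation that allows for deaths gives 1.6-4.7 (all localized) and 5.1-7.5 (75% localized). With 15% early stops these become 1.5-4.4 and 4.7-6.9.

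**4. Precision with no bias.** With an assumed 1%/year mortality before and after progression, the SD of 24-month OS is 3.5 points if all 16 are followed. Under footnote 12 it is 5.4-7.4 (all localized) or 4.4-5.2 (75% localized). If no deaths occur in months 13-24 among k patients followed, the one-sided 95% upper limit for the risk of death is 1 - 0.05^(1/k): 17% for k = 16, 45% for k = 5, 78% for k = 2.

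**5. Bias if mortality rises after progression.** Worked case, all localized: q = 20% by 12 months, so the progression rate is L = -ln(0.8) = 0.2231/year. Assumed mortality is 0.01/year before and h = 0.10/year after progression. With a = L + 0.01 = 0.2331,

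S(t) = exp(-a t) + [L/(a - h)] x [exp(-h t) - exp(-a t)].

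- S(13 months) = 0.979 and S(24 months) = 0.948; the latter is what full follow-up estimates.
- Under footnote 12, only progressors contribute after month 13, so the estimate tends to 0.979 x exp(-0.10 x 11/12) = 0.979 x 0.912 = 0.893.
- Bias: 0.893 - 0.948 = -5.5 points.

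The same formula for q = 10-30%, beside simulated trials of 16 with the curve carried forward when nobody is at risk:

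| Mortality after progression | Formula (points) | Simulated (points) |
|---|---|---|
| 1%/year (equal) | 0 | about 0 |
| 2%/year | -0.5 to -0.8 | -0.4 to -0.6 |
| 5%/year | -2.0 to -3.0 | -2.1 to -2.4 |
| 10%/year (extreme for localized disease) | -4.5 to -6.6 | -4.4 to -5.2 |

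With 75% localized (advanced: 70% progression by 12 months, assumed), simulated bias is -1.9 to -3.4 points at 2%/10% per year after progression (localized/advanced), -4.8 to -8.5 at 5%/25%, and -7.6 to -12.9 at 10%/40% (extreme). Reading the rates as annual probabilities and fixing the mix at 12 and 4 gives somewhat larger values, down to -16.2. In the main simulation the bias is below one standard error of full follow-up (3.6-8.8 points) in 14 of 18 unequal-mortality scenarios.

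**The case against.** **The harm falls on an analysis that nobody planned.** Section 8 names no Kaplan-Meier OS estimate and no 24-month time point. An analyst could report OS to about month 12-13, or by disease extent, largely without this bias. This stands, and it is why restricting OS reporting is an acceptable alternative.

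**The size is hypothetical.** Progression rates, mortality and case mix are all assumed. Section 3.1 says of the localized tumors that "they are not expected to pose a risk of metastatic spread when the size of the tumors is <3cm", so few deaths are likely in that group. The simulation carries the curve forward when nobody is at risk; with 10% progression and all localized, 0.9^16 = 18.5% of trials have no progressor. It also counts progression only on treatment, although footnote 12 is not limited to that. These points stand as limits on the figures. The formula, which needs no carry-forward, gives the same direction and similar or larger sizes.

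**Vital status may be obtainable anyway.** Section 10.5 says most patients need lifelong surveillance, and Section 7.3.1 requires reporting of deaths other than those due to progression, with no time limit. Both narrow the gap. Neither sets a contact schedule, and the second depends on the investigator learning of the death.

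**Footnote 12 does not forbid contacting others.** True, but nothing else schedules it.

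**PFS.** A reader might infer that the absence of a PFS time horizon is itself an error. The documents do not support that: a time-to-event endpoint can end at progression, death or censoring without a fixed horizon, and scheduled scans cover the first 52 weeks for patients who stay on treatment.

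**Conclusion.** The point holds as a cheap improvement to a secondary objective. On the text, scheduled OS follow-up beyond about week 56-57 depends on progression and on still being treated; patients who stop early without progressing leave it sooner. Late OS is biased downward if mortality is higher after progression, and unbiased but imprecise if it is not. The size cannot be fixed from the documents and is probably small in localized disease; the larger values need assumed high mortality after progression in advanced disease.

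Two stronger readings are not supported. One is that late OS is known to rest on a small group: the range is 1.6 to 7.5 of 16, nearly half the trial at the upper end, and depends on inputs the documents do not give. The other is that the trial's conclusion is at risk: the response endpoint and the rule of 3 responders are untouched.

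**What to change.** **Survival contact.** Amend footnote 12 so that contact every 3-6 months applies to every treated patient from end of treatment, regardless of progression, to one common cut-off. Use that cut-off to define the follow-up period in Section 3.6.2. Two options, with 18 patients at the fastest stated accrual of one per month (first doses at months 0-17):

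| Cut-off | Study month | Contacts if all 18 complete the year |
|---|---|---|
| Last localized patient's EOT+28-day visit | 17 + 13 = 30 | 21-51 |
| 24 months from first dose | 17 + 24 = 41 | 18 x (12/6) = 36 to 18 x (12/3) = 72 |

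The first can fit the 2-3 years in Section 8, with potential follow-up of 13-30 months (median 21.5). The second runs past it if that figure means total duration. Slower accrual lengthens both. Contacts with progressors are already planned, so fewer are new; no visits or scans are added. If neither option is wanted, limit OS reporting to about 12-13 months or drop OS as an objective.

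**PFS.** Apply any 52-week limit only to localized patients. Keep the scheduled on-treatment scans after week 52 for patients treated until progression. State how deaths, and early stops without progression, are handled; censoring patients who stop for toxicity may itself be informative.

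**Reconcile.** Sections 3.1 and 3.4 differ on whether locally advanced patients fall under the 52-week limit. Table 3-2 removes some patients with unresolved toxicity from the study, whereas Section 3.6.1 lists toxicity as a reason to leave therapy and Section 3.6.2 does not list it as a reason to leave the study. Both pairs must be reconciled so that it is clear who remains in follow-up. No clinical rule is proposed here.

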3.5 FOLLOW UP EVALUATIONS

After subjects have stopped taking the study medication for any of the reasons listed in Section **3.6.1**, they will be seen at NIH, if feasible, for a safety visit within 4-5 weeks of drug discontinuation. The safety assessments may be performed by a local physician and laboratory if patients unable to return to the NIH Clinical Center at this time.

The following assessments may be completed at the end of treatment +28 days; every effort will be made to complete the following whenever feasible and the patient can comply:

- History and Physical Examination
- Serum Chemistries and CBC/Diff
- HBV DNA, HCV RNA-PCR if indicated

If there are unresolved grade 3 – 4 AEs, patients will be followed either at the NIH clinical center or by their local physician. In the latter case, we will obtain the physician’s record of AEs.

Any scans performed outside of the NIH will also be obtained when possible.

3.6 CRITERIA FOR REMOVAL FROM PROTOCOL THERAPY AND OFF STUDY CRITERIA

Prior to removal from study, effort must be made to have all subjects complete a safety visit approximately 28 days following the last dose of study therapy.

3.6.1 Criteria for removal from protocol therapy

- Completion of protocol therapy.
- Progressive disease
- Participant requests to be withdrawn from active therapy
- Unacceptable Toxicity as defined in Section **6.2**.
- Investigator discretion
- Positive pregnancy test

3.6.2 Off-Study Criteria

- Completed study follow-up period
- Patient lost to follow-up
- Investigator discretion
- Participant requests to be withdrawn from study
- Death

Abbreviated Title: Phase II everolimus for BHD

Version Date: March 7, 2017

3.6.3 Off-Study Procedure

Authorized staff must notify Central Registration Office (CRO) when a subject is taken off-study. An off-study form from the web site

(<http://home.ccr.cancer.gov/intra/eligibility/welcome.htm>) main page must be completed and sent via encrypted email to: NCI Central Registration Office (HOIS) [contact].

4 CONCOMITANT MEDICATIONS/MEASURES

Patients must be instructed not to take any medications (over-the-counter or other products) during the protocol treatment period without prior consultation with the investigator. The investigator should instruct the patient to notify the study site about any new medications he/she takes after the start of study drug. All medications (other than study drug) and significant non-drug therapies (including physical therapy and blood transfusions) taken within 28 days of starting study treatment through the 30-day safety follow up visit should be reported on the CRF.

Use of anti-neoplastic or anti-tumor agents not part of the study therapy, including chemotherapy, radiation therapy, immunotherapy, and hormonal anticancer therapy, is not permitted while participating in this study. If indicated, a bisphosphonate or denosumab may be used.

4.1 PERMITTED CONCOMITANT THERAPY

4.1.1 Cytochrome P450 and P-glycoprotein inhibitors/inducers/substrates

Co-administration with strong or moderate inhibitors of CYP3A4 or PgP should be avoided as this may cause increased everolimus concentrations. For a current table of Substrates, Inhibitors and Inducers please access the following website:

<http://www.fda.gov/Drugs/DevelopmentApprovalProcess/DevelopmentResources/DrugInteractionsLabeling/ucm093664.htm>

Everolimus is metabolized by CYP3A4 in the liver and to some extent in the intestinal wall.

Therefore, the following are recommended:

- Co-administration with strong or moderate inhibitors of CYP3A4 (e.g., ketoconazole, itraconazole, ritonavir) or P-glycoprotein (PgP) inhibitor should be avoided.
- Grapefruit, Seville oranges, and starfruit affect P450 and PgP activity. Concomitant use should be avoided.
- Co-administration of a strong CYP3A4 inducer should be avoided.
- Please refer to Table 4-1 listing relevant inducers and inhibitors of CYP3A and Table 4-2 for a list of relevant substrates, inducers, and inhibitors of PgP.

4.1.2 Everolimus and drugs influencing CYP3A4 enzyme

Everolimus is a substrate of CYP3A4, and a substrate and moderate inhibitor of the multidrug efflux pump, PgP (PgP, MDR1, and ABCB1). Therefore, extent of absorption and subsequent

Abbreviated Title: Phase II everolimus for BHD

Version Date: March 7, 2017

elimination of systemically absorbed everolimus may be influenced by products that are substrates, inhibitors, or inducers of CYP3A4 and/or PgP. Concurrent treatment with strong or moderate CYP3A4-inhibitors should be avoided. Refer to Table 4-1 for a comprehensive list of inducers and inhibitors of CYP3A4 and Table 4-2 for a list of relevant substrates, inducers and inhibitors of PgP. Inhibitors of PgP may decrease the efflux of everolimus from brain or tumor and therefore increase everolimus concentrations in these tissues. In vitro studies showed that everolimus is a competitive inhibitor of CYP3A4 and of CYP2D6, potentially increasing the concentrations of products eliminated by these enzymes. Thus, caution should be exercised when co-administering everolimus with CYP3A4 and CYP2D6 substrates with a narrow therapeutic index. Clinical studies have been conducted in healthy subjects to assess pharmacokinetic drug interactions between everolimus and potential CYP3A modifiers (ketoconazole, verapamil, erythromycin, rifampin, midazolam, and HMGCoA reductase inhibitors (statins).

Table 4-1: Clinically relevant drug interactions: inducers, and inhibitors of isoenzyme CYP3A

Inducers
carbamazepine, glucocorticoids, modafinil, oxcarbazepine, phenobarbital, phenytoin, pioglitazone, rifabutin, rifampin, St. John's wort, troglitazone, efavirenz, nevirapine, topiramate, avasimibe, bosentan, etravirine, naftcillin, ritonavir, talviraline (not available in US market), tipranavir, amprenavir, aprepitant, armodafinil (R-modafinil), dexamethasone, nevirapine, prednisone, pleconaril (not available in US market), rufinamide
Inhibitors
Strong inhibitors: clarithromycin, conivaptan, indinavir, itraconazole, ketoconazole, lopinavir, mibepradil, nefazodone, nelfinavir, ritonavir, saquinavir, telithromycin, troleandomycin, voriconazole, tipranavir, elvitegravir, Posaconazole ³¹
Moderate inhibitors: aprepitant, atazanavir, casopitant, cimetidine, ciprofloxacin, darunavir, diltiazem, erythromycin, fluconazole, grapefruit juice (citrus paradisi fruit juice), imatinib, tofisopam, verapamil, amprenavir, fosamprenavir, dronedarone

Table 4-2: Clinically relevant drug interactions: substrates, inducers, inhibitors of PgP and PgP/CYP3A dual inhibitors

Abbreviated Title: Phase II everolimus for BHD

Version Date: March 7, 2017

Substrates
digoxin, fexofenadine, indinavir, vincristine, colchicine, topotecan, paclitaxel
Inducers
rifampin, St John's wort
PgP Inhibitors and PgP/CYP3A Dual Inhibitors
amiodarone, captopril, carvedilol, clarithromycin, conivaptan, diltiazem, dronedarone, elacridar, erythromycin, felodipine, fexofenadine, ginkgo (ginkgo biloba), indinavir, itraconazole, , lopinavir, mibepradil, milk thistle (silybum marianum), nifedipine, nitrendipine, quercetin, quinidine, ranolazine, ritonavir, saquinavir, Schisandra chinensis, St John's wort (hypericum perforatum), talinolol, telmisartan, tipranavir, valsopdar, verapamil
Reference: Internal Clinical Pharmacology Drug-drug interaction (DDI) memo, updated Oct. 2, 2011, which summarizes DDI data from three sources including the FDA's "Guidance for Industry, Drug Interaction Studies", the University of Washington's Drug Interaction Database, and Indiana University School of Medicine's Drug Interaction Table.

